i) Pharmacological intervention: After the baseline studies, subjects will be randomized to metformin (titrated up to 1000 mg twice daily, as tolerated) vs. placebo over a period of 6 months. Metformin and placebo are obtained from Major Pharmaceuticals (Livonia, MI). Randomization and drug preparation and dispensing will be performed by the Research Pharmacist of the BRU. Subjects will be initiated at 500 mg daily at Visit 2. Subjects will be seen in person at 1 week, and if tolerating metformin, will be directed to increase to 500 mg twice daily after 2 weeks. Phone calls will be made about every two weeks to titrate medications as tolerated as needed until patient is at maximum dose tolerated with goal dose of 1000 mg twice daily. At 3 months subjects will be seen in-person for a history & physical examination. OGTT will be performed every 6 months to monitor for diabetes conversion. Plasma metformin level will be measured once the participant has reached his/her maximum tolerated dose at either Visit 2, 4, 5, 6, 7, 8, 10, 11, 12, 13 or 14. If participants convert to diabetes and are started on metformin from placebo, an additional metformin level will be measured once the patient has reached his/her maximum tolerated dose at either Visit 2, 4, 5, 6, 7, 8, 10, 11, 12, 13, or 14. All patients will also receive patient education handouts about lifestyle modification to prevent diabetes at Visit 2.

j) Diet and exercise counseling: After the baseline visit, subjects will receive standard diet and exercise advice using resources available from the National Institute on Aging. This will be conducted by study staff member, [name], who is a certified diabetes educator. Resources will be given to subjects, including "Exercise & Physical Activity: Your Everyday Guide from the National Institute on Aging" available from <https://www.nia.nih.gov/health/publication/exercise-physical-activity/introduction>, and "What's On Your Plate? Smart Food Choices for Healthy Aging" available from <https://www.nia.nih.gov/health/publication/whats-your-plate>.

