k) Management of conversions: Any one of the following will prompt 2-hour OGTT to confirm possible diagnosis of diabetes: fasting glucose  $\geq$  126 mg/dL, HbA1c  $\geq$  6.5%, 2-hour OGTT glucose of  $\geq$  200 mg/dL, or clinical signs and symptoms of diabetes. If any of these occur, OGTT will be conducted within 6 weeks. If the subsequent 2-hour OGTT glucose is  $\geq$  200 mg/dL, diabetes conversion will be confirmed. If diabetes conversion occurs based on the OGTT, measurements of frailty, insulin sensitivity (clamp), body composition (DEXA), coagulation tests, stool sample, and inflammation (muscle and systemic) will be

performed. If these assessments are conducted within 1 month of the 12 month or 24 month assessments, the 12 or 24 month assessments will not be conducted. After these repeat measurements are performed, the study allocation will be unblinded, and, if receiving placebo, subjects will be initiated on metformin and titrated as above. Medication management will occur by an independent practitioner (MD or NP) on the study staff who is not the PI such that the PI will remain blinded to study treatment. Hemoglobin A1c will be monitored in those who have converted to diabetes, and, if it reaches  $\geq 7.5$ , subjects will be initiated on 15 mg pioglitazone in addition to metformin unless there is a contraindication to pioglitazone. The rationale for adding pioglitazone versus other antidiabetic agents is that the low dose metformin-thiazolidinedione combination has been shown to have a potent effect to prevent diabetes (Zinman et al., 2010). Pioglitazone will be increased to 30 mg if hemoglobin A1C remains  $\geq 7.5$ . Pioglitazone will not be initiated in any subject with the following: hematuria, history of bladder cancer, lower extremity edema  $> 1+$ , or known history of osteopenia or osteoporosis. Subjects will be seen every 3 months for monitoring of HbA1C. If maximal metformin (1000 mg BID) and pioglitazone (30 mg daily) doses are reached (or if the patient cannot tolerate metformin and/or pioglitazone) and HbA1C remains  $\geq 8$ , subjects will be referred to their primary care physicians for further treatment, but will remain in the study for frailty assessment and all other follow-up studies. Subjects who initially were on metformin will receive pioglitazone 15 mg (in addition to metformin) if Hemoglobin A1c reaches  $\geq 7.5$ , which will be titrated to 30 mg if necessary as described above.

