#### Data Analysis Plan:

### STATISTICAL METHODS & POWER CALCULATIONS

**Overview.** In all analyses for Aim 1 and Aim 2, primary inference will be drawn based on intention to treat (ITT) analyses. Average complier effect (ACE) will be used to inform the metformin effect under full compliance to treatment assignments (Angrist et al, 1996). Per protocol analyses will be used to inform the metformin effect among completers. All analyses will be carried out unadjusted and with adjustment for covariates (Table 7) and covariate interactions with treatment and time. Corrections for multiple comparisons will be applied as appropriate.

The impact of metformin treatment on the progression of frailty status (non-frail, pre-frail, frail) over time will be assessed with a repeated measures mixed effects multinomial logistic model that models the log-odds of adjacent frailty statuses in terms of an indicator of metformin use, time, and the metformin use by time interaction. The possibility of non-linear trends of the log-odds of frailty statuses will be assessed by including an additional time factor (e.g., time squared) and its interaction with metformin use. The best fitting model will be used for inference. Secondary outcomes including gait speed, 6 minute walk, SPPB, frailty index constructed from the research data collected according to the Rockwood index (Searle et al., 2008; Rockwood et al., 2007), and body composition will similarly assessed. Under the linear trend model, the beneficial impact of metformin will be revealed by a significant time by treatment interaction associated with the log-odds of frailty status progression, indicating that the rate of increase in the likelihood of frailty progression over time is reduced in the metformin arm relative to the placebo arm. Under the non-linear trend model, the impact of metformin will be revealed by a significant reduction in the log-odds of frailty status progression in the metformin arm versus placebo at certain time points during the follow-up. SAS proc **nlmixed** will be used in the mixed effects model analyses. Proc **nlmixed** is preferred over other mixed effects modeling procedures such as GEE because it is valid under missing at random (MAR) assumption, accommodates linear and non-linear modelling, and uses maximum likelihood estimation.

Table 7. Covariates included in statistical analyses

Categories of covariates	Baseline	Time Varying
Demographics (age, sex)	X	
BMI (obesity), sarcopenia	X	X

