Lipids, blood pressure	X	X
Fasting glucose, HbA1c, Insulin Sensitivity from OGTT (Matsuda) and Insulin Clamp	X	X
Inflammation (systemic & muscle), Insulin Signaling (muscle)	X	X
Diabetes conversion		X
Pioglitazone use		X

Of secondary interest, a per protocol analysis will be carried out with restriction to patients who follow the protocol throughout the study, and where those who drop out, violate the protocol or change treatments are excluded. Separately, those who change treatments will be summarized and described. To account for any treatment change, we will also consider principal stratification analysis (which requires categorization of patients based on treatment change patterns) and marginal structural modeling (which obtains the overall metformin effect accounting for treatment change, and time-varying covariates (e.g., diabetes status), and outcomes (e.g. frailty, physical function) history.

Metformin dose will be handled in the statistical analysis by conducting dose-response analysis among metformin users. Several options of metformin dose/exposure variables will be considered in separate analyses: average daily dose, clinical meaningful threshold for average daily dose, total days of supply, and clinical meaningful threshold for total days of supply. Should there be any discrepancy among these dose-response analyses, we will reconcile these results for the final interpretation.

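### The metformin dose-response analysis uses an undefined user population and un-lagged exposure summaries, so with no drug effect it can show a spurious trend in either direction

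*Combined protocol and SAP*

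**What the plan says.** The dose paragraph of the Data Analysis Plan (Item 6, Overview) reads: "Metformin dose will be handled in the statistical analysis by conducting dose-response analysis among metformin users". The exposures, each to be analysed separately, are "average daily dose, clinical meaningful threshold for average daily dose, total days of supply, and clinical meaningful threshold for total days of supply". Any disagreement between these analyses is to be reconciled for the final interpretation, with no rule given. The paragraph does not define a user. It states no exposure window, no denominator for the average, no lag, no time-updating and no outcome model.

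Four other places bear on it:

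- Study Procedures, i) Pharmacological intervention: dose is raised stepwise only as far as each participant tolerates it.
- Potential risks, item 7 (Administration of metformin): participants who do not tolerate metformin are disenrolled.
- Study Procedures, k) Management of conversions: after confirmed diabetes and unblinding, "if receiving placebo, subjects will be initiated on metformin and titrated as above". Section i) adds: "If participants convert to diabetes and are started on metformin from placebo, an additional metformin level will be measured".
- Overview: "All analyses will be carried out unadjusted and with adjustment for covariates (Table 7) and covariate interactions with treatment and time". Table 7 lists diabetes conversion as a time-varying covariate. The Overview also makes intention to treat the basis of primary inference.

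**The concern.** Days of supply is a sum over a participant's time on drug. Unless it is cut off before the outcome, it includes supply dispensed, or not dispensed, after frailty has worsened. A participant who worsens and then stops or reduces drug ends with low exposure and a bad outcome, which looks like protection by metformin. A participant who leaves early has low exposure and little time in which worsening could be seen, which looks like harm. Neither pattern needs any drug effect, and both arise within the randomised metformin arm.

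A second problem depends on how users is read. Placebo participants who convert to diabetes start metformin late, so their supply is short, and all of them have diabetes, which the plan's own background links to frailty progression. If they count as users, low exposure is tied to higher frailty risk by design.

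This is the plan's only handling of dose. A trend in either direction could be taken as evidence about metformin when it reflects timing.

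**Working it through.** **Stated figure.** The plan gives no effect size, power or expected result for this analysis, so there is nothing to reproduce. The check is whether the stated exposures give a null answer when the truth is null.

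**Inputs from the documents.** 60 completers per arm (3.D.3); 24 months; glucose tolerance test every 6 months; 47-58% worsening (Aim 1 design text; 52% used); two-sided 5%, hence 2.5% in each direction; diabetes odds ratio 1.84 for gaining a frailty characteristic (Preliminary Data) and 1.40 for incident frailty (Background); dropout 4-5% (Aim 1 design text).

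**Assumptions not in the documents.** Two-year conversion of 10%, 20% or 30%, spread evenly over months 6, 12, 18 and 24; mean adherence 90%; final dose unrelated to frailty; the stopping, dose-reduction and higher dropout rates below.

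**Model.** logit P(worsening) = a + b × exposure, one record per person; exp(b) should be 1. This stands in for the outcome model that the paragraph does not name. There were 2,000 simulated trials per scenario, with large samples used for bias. Where two simulation set-ups differing in detail gave a rate, the range is shown.

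**1. Randomised metformin arm only, total days of supply.** About 60 × 0.52 = 31 people worsen, so 10% stopping is about 3 people and 25% about 8.

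| Scenario under the null | Significant protection | Significant harm |
|---|---|---|
| No stopping, no dropout | 2.3% | 2.2% |
| 10% of those who worsen stop | 6.5-8% | 0.5% |
| 25% of those who worsen stop | 35-46% | 0% |
| 5% random dropout | 0.5% | 4.7% |
| 15% random dropout | 0% | 17-22% |

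Large-sample odds ratios per year of supply are 1.04 (no stopping or dropout), 0.095 (25% stop) and 4.4 (15% dropout). A full year is a wide contrast within one arm, so the error rates are the better guide.

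**2. Dose reduction instead of stopping.** If 20-50% of those who worsen have their dose lowered by 500 mg/day, whole-study average dose gives odds ratios of 0.73 to 0.48 per g/day in the randomised arm under the null. Dose in the interval before each visit, in a discrete-time model of worsening, gives 0.99-1.00.

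**3. If switched placebo participants count as users.** Their supply is at most 24 − 6 = 18 months. At 20% conversion, 60 × 0.20 = 12 convert and 12 × 3/4 = 9 do so early enough to accrue supply; at 10% and 30% the numbers are about 5 and 14. Pooled with the randomised arm, with no stopping or dropout:

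- Days of supply, unadjusted, 20% conversion: odds ratio per year 0.66 (diabetes odds ratio 1.84) or 0.78 (1.40).
- Significant protection: 2.7%, 4.5% and 6.7% of trials at 10%, 20% and 30% conversion (1.84); 1.7% and 2.9% at 10% and 20% (1.40).
- Adjusted for conversion: odds ratio 0.98; significant protection in about 1.5-2%.
- Average dose at 20% conversion and 1.84: 0.80 per 1000 mg/day over 24 months, but 1.00 over on-drug days.

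**4. Does adjusting for conversion deal with the timing problem?** No. With 25% stopping, the pooled analysis adjusted for conversion still shows significant protection in 26% of trials.

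**The case against.** The strongest reply is that the plan does not say what a critic might assume. A reader might infer that the analysis pools switched placebo participants with the randomised arm and would therefore show a protective dose-response even if metformin did nothing. The documents do not support this:

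- Pooling is never stated. The Aim 1 model is written "in terms of an indicator of metformin use, time, and the metformin use by time interaction", where metformin use plainly means the arm, and those who change treatment are to be summarised separately. A randomised-arm reading is open.
- The planned adjustment for conversion removes most of the switching bias, and switching alone barely raises the error rate at 60 per arm.
- The direction is not fixed, because dropout pushes towards apparent harm.
- The 1.84 concerns diabetes in an observational cohort, not conversion newly found on a glucose tolerance test. With 1.40 the error rate stays near nominal.

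All of that stands. So does the point that averaging over on-drug days avoids the stopping and dropout biases (odds ratios 0.99 and 1.01), although it does not avoid the dose-reduction bias in step 2, and the plan does not choose that denominator. At the stated 4-5% dropout, the push towards harm is small. It also depends on the person-level model: a visit-level model with a time term should suffer less from dropout.

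What the reply does not remove is the timing fault. It occurs inside the randomised arm, so it does not depend on how users is read. Adjusting for conversion does not address it. Marginal structural modelling is only to be considered, and for the overall effect under treatment change, not for dose.

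**Conclusion.** The concern holds in this form: the population is undefined, and the named exposures, with no lag, can produce a spurious trend in either direction when metformin has no effect on frailty. The size depends mainly on how often participants who worsen stop or reduce drug, which the documents do not give. At an assumed 10% the protective error rate is 6.5-8%; at 25% it is 35-46%. Random dropout of 15% gives false harm in 17-22%.

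Switching is a secondary, conditional problem. It biases the unadjusted result to about 0.66-0.78 per year of supply at an assumed 20% conversion, but adds little error at this sample size and is largely removed by the planned adjustment. That adjustment is not a full safeguard, since it conditions on a post-baseline event that metformin may affect.

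The inference that the plan will show protection regardless of truth should not be drawn. Primary inference is intention to treat and the dose analysis is supportive, so this should be corrected but does not threaten the main result.

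**What to change.** In the dose paragraph of the Data Analysis Plan:

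1. Restrict the dose-response analysis to participants randomised to metformin.
2. Relate frailty at each visit to the dose dispensed in the preceding interval, or to cumulative dose up to the previous visit, adjusted for baseline frailty score and age. The near-null result in step 2 of the working came from modelling worsening interval by interval. If frailty status at every visit is modelled instead, also condition on the score at the start of the interval, because an earlier worsening can both persist and change the dose.
3. Drop whole-study total days of supply, and its threshold version, as exposures.
4. Describe switched placebo participants separately.
5. Label the result non-randomised and supportive.

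The cost is SAP wording and a little programming. The few switched participants are lost to this analysis, and confounding by tolerability remains and should be stated.

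A side point, not needed for this conclusion: section i) says "Plasma metformin level will be measured once the participant has reached his/her maximum tolerated dose at either Visit 2", yet dosing also starts at Visit 2. The two statements should be reconciled.

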**3.D.4. Aim 2.** To address the question as to whether an anti-frailty effect of metformin is mediated by its insulin sensitizing and anti-inflammation effects, we will employ the unified mediation analysis framework by Vanderweele. Insulin sensitivity (Matsuda index derived from the OGTT) will be measured at baseline, 6, 12, 18 and 24 months, and 8 biomarkers of systemic inflammation (IL-6, CRP, TNFa, IL-1RA, TNFs R1 and 2, fibrinogen, and transferrin), insulin sensitivity (clamp) and multiple biomarkers of muscle inflammation and insulin signaling (NF $\kappa$ B and MAPK signaling, and mRNA levels of inflammatory cytokines) will be measured at baseline, 12 months, and 24 months. First, we will conduct separate repeated measures mixed effects linear model analyses to assess the effect of metformin treatment on each insulin sensitivity and inflammation measure. In each of these analyses, the outcome (or its normal transformation) will be modelled in terms of an indicator of metformin treatment, time, the treatment by time interaction, and covariates. The coefficient associated with the treatment by time interaction will inform the effect of metformin on the temporal change of each biomarker. We will then conduct repeated measures mixed effects multinomial logistic model to assess whether the odds of an increase in the frailty score is associated with the change in insulin sensitivity from baseline to 24 months ( $\Delta$ IS), and change in inflammation from baseline to 24 months ( $\Delta$ I) by modelling the log-odds of frailty worsening in terms of metformin treatment, time,  $\Delta$ IS,  $\Delta$ I, (metformin) treatment $\times$ time, and covariates. The treatment $\times$ time $\times$  $\Delta$ IS and treatment $\times$ time $\times$  $\Delta$ I interactions will be explored to assess whether metformin attenuates the effect of  $\Delta$ IS and  $\Delta$ I: this effect will be revealed by a significant coefficient associated with treatment $\times$ time $\times$  $\Delta$ IS or treatment $\times$ time $\times$  $\Delta$ I. If some  $\Delta$ IS and  $\Delta$ I measures are collinear, then we will model the odds of frailty worsening in terms of  $\Delta$ IS and  $\Delta$ I separately. All of these analyses will be initially carried out for a pair of an inflammation biomarker and an insulin sensitivity marker separately. Aim 2 will be verified in principle if (i) metformin is associated with significant increase in  $\Delta$ IS and decrease in  $\Delta$ I; and (ii) frailty worsening is

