
associated with significant decrease in  $\Delta IS$  and increase in  $\Delta I$ ; and (iii) the indirect effects of metformin (mediated by  $\Delta I$  and  $\Delta IS$ ) calculated based on Vanderweele are significant.

**3.D.5. Power Calculation for Aim 2. Inflammation.** A 3 month clinical trial of insulin sensitizers versus placebo in patients with impaired glucose fasting glucose or diabetes found decreased TNF $\alpha$  in treated patients (effect size =1.5) . Assuming the same or larger decrease in TNF $\alpha$ , 60 completers in each group, 6 repeated measures, autocorrelation 0.5, and overall type 1 error of 0.05, we expect to have power  $\geq 95\%$  to detect a group difference with regard to mean TNF $\alpha$  and power  $\geq 95\%$  power to detect an increase in TNF $\alpha$  and frailty worsening in the combined cohort [PASS Version 11, NCSS Kaysville UT 2011]. **Insulin sensitivity.** The Diabetes Prevention Program demonstrated improved fasting glucose in metformin treated adults (decrease of 4.1 mg/dL) with pre-diabetes and increased fasting glucose (by 0.4 mg/dL) in placebo group . Assuming the same treatment effect on fasting glucose in this study, and n=60 completers per arm, this study will attain a power of 80% for testing the null hypotheses of no treatment effect, two sided testing, 6 repeated measures, and an autocorrelation of 0.5 [PASS Version 11, NCSS Kaysville UT 2011].

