**3.D.6. Time to major adverse event.** The relation between treatment and time to major adverse outcome will be studied with and without adjustment for covariates and will be described with Kaplan-Meier curves. An adverse outcome will be defined as a) 2 point increase in the frailty score, or b) fall resulting in bone fracture or other serious injury, c) admission to a nursing home or skilled care facility, or d) death. The time to adverse outcome will be defined as the time to first occurrence of any of a), b), c) or d) and will otherwise be considered censored at loss to follow-up or end of study. Without adjustment, treatment groups will be contrasted on time to major adverse outcome with a logrank test and the treatment-specific accumulated incidence of adverse outcome will be described with Kaplan-Meier curves and 95% confidence bands. An adjusted contrast of treatment groups will be carried out with a Cox proportional hazards model in terms of treatment group, age, ethnicity, gender, and baseline values of frailty score. OGTT and inflammatory biomarkers will be entered as time-dependent covariates. Logrank testing, Kaplan-Meier estimates of survival distributions, and covariate adjusted Cox modelling of relative risks accommodate non-informative right censored survival data.

**3.D.7. Missing Data.** Limited missingness in outcomes and associated covariates is possible due to loss to follow-up. Missing covariates without loss to follow-up may occur due to missed appointments and intercurrent illness. In the primary analyses, model estimates will be derived based on the likelihood of observed data, an approach that gives consistent estimates under the MAR assumption: “missingness” depending upon the observed data but not the unobserved. To further address the possibility of missing data under the MAR assumption, we will conduct all analyses without and with multiple imputation using SAS proc mianalyze and its companion procedure proc mi. The mianalyze procedure combines the results of the analyses of imputations and generates valid statistical inferences and MI creates multiply imputed data sets for incomplete multivariate data.

**3.D.8. Randomization.** Participants will be randomized to metformin or placebo in a balanced design.

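### The Aim 2 biomarker models and the continuous secondary models spend precision on a baseline arm difference that randomisation makes zero in expectation; at the plan's only stated correlation (0.5) the loss on treatment × time is about 25–52%

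*Combined protocol and SAP*

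**What the plan says.** **First-step models.** In section 3.D.4 each insulin-sensitivity and inflammation measure, transformed if needed, is "modelled in terms of an indicator of metformin treatment, time, the treatment by time interaction, and covariates". The metformin effect is read from one term: "The coefficient associated with the treatment by time interaction will inform the effect of metformin on the temporal change of each biomarker". The Matsuda index is measured at 0, 6, 12, 18 and 24 months. Clamp, muscle and plasma markers are listed at 0, 12 and 24 months, although the follow-up section and visit table put plasma markers on a six-monthly schedule. Baseline is therefore one of the modelled outcome values.

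**Secondary outcomes.** The Overview of the statistical methods gives the frailty model the same three terms and continues: "Secondary outcomes including gait speed, 6 minute walk, SPPB, frailty index constructed" from research data, "and body composition will similarly assessed".

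**Randomisation.** Section 3.D.8: "Participants will be randomized to metformin or placebo in a balanced design". The intervention paragraph of Item 6 places randomisation after the baseline studies.

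**Covariates.** The Overview runs every analysis both without covariates and with those of Table 7 and their interactions with arm and time. Neither is named as primary. Table 7 lists insulin sensitivity, inflammation and insulin signalling as both baseline and time-varying covariates. It does not list gait speed, 6-minute walk, SPPB or the frailty index.

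**Correlation.** The only value is in section 3.D.5: "60 completers in each group, 6 repeated measures, autocorrelation 0.5, and overall type 1 error of 0.05" for TNFα, and "6 repeated measures, and an autocorrelation of 0.5" for fasting glucose. No covariance structure is named.

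**The concern.** With time counted from baseline, the treatment main effect is the arm difference before any study drug is taken. Its expectation is zero by design. If it is left free, chance imbalance at baseline has to be estimated and is subtracted from the treatment effect, much as in a change-from-baseline analysis. The treatment × time coefficient bears the cost.

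The trial plans about 60 completers per arm, and the clamp and biopsy measures are invasive and taken three times at most on the regular schedule. Section 3.D.4 counts Aim 2 as supported only if, among other conditions, metformin significantly changes both insulin sensitivity and inflammation. Precision in these first-step models therefore bears directly on the plan's own success rule, and the lost part can be regained from data already being collected.

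**Working it through.** **The plan's own figures.** The TNFα power of at least 95% reproduces: an effect size of 1.5 with 60 per arm gives 1.5 × √30 = 8.2 standard errors, so power exceeds 99.9% even from one measure. The 80% for fasting glucose (difference 4.1 + 0.4 = 4.5 mg/dL) cannot be checked because no SD is given. It implies an SD of 8.8 mg/dL for a single measure, or 11.5 (equal correlation) or 14.1 (AR(1)) if the mean of six measures is tested. Neither calculation is shown to be for treatment × time.

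**Inputs.** Visits at 0/12/24 months or 0/6/12/18/24 months (3.D.4); correlation 0.5 and 60 per arm (3.D.5); equal allocation (3.D.8). Assumptions: complete data, unit variance at every visit, time x running linearly from 0 to 1, and either equal correlation or AR(1) with 0.5 between adjacent visits.

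**Formulas.** With V the within-person covariance, generalised least squares information on treatment × time is, up to a common factor:
- baseline difference free: x′V⁻¹x − (1′V⁻¹x)² / (1′V⁻¹1)
- baseline difference fixed at zero: x′V⁻¹x
- share lost: 1 − free / fixed; variance factor: fixed / free

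| Visits | Structure | x′V⁻¹x | 1′V⁻¹x | 1′V⁻¹1 | Free | Factor | Lost |
|---|---|---|---|---|---|---|---|
| 3 | equal | 1.3750 | 0.7500 | 1.5000 | 1.0000 | 1.38 | 27% |
| 3 | AR(1) | 1.0833 | 0.8333 | 1.6667 | 0.6667 | 1.62 | 38% |
| 5 | equal | 1.6667 | 0.8333 | 1.6667 | 1.2500 | 1.33 | 25% |
| 5 | AR(1) | 1.1250 | 1.1667 | 2.3333 | 0.5417 | 2.08 | 52% |

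First row: 1.3750 − 0.75²/1.5 = 1.0000, and 1 − 1.0000/1.3750 = 0.27. At three visits, 60 per arm with a common baseline is as precise as 60 × 1.375 ≈ 82 to 60 × 1.625 ≈ 98 per arm in the planned model.

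**Categorical visits.** At month 24 the change score has variance 2(1 − r) and the baseline-adjusted contrast 1 − r², where r is the baseline-to-month-24 correlation. The share lost is (1 − r)/2: 25% at r = 0.5, 38% at r = 0.25 (AR(1), 3 visits) and 47% at r = 0.0625 (AR(1), 5 visits).

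**Sensitivity (linear time, 3 and 5 visits).**
- Equal correlation: 39–40% at 0.3, 14–16% at 0.7, 4–5% at 0.9.
- AR(1): 49–60% at 0.3, 26–39% at 0.7, 10–17% at 0.9.
- Random slopes added to equal correlation 0.5, with slope variance assumed at 0.25 to 0.5 of the baseline variance: 15–22%.

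**Does covariate adjustment recover it?** In 400 simulated trials at equal correlation 0.5, adding the outcome's own baseline as a main effect left the variance unchanged (0.0298 against 0.0298 at 3 visits; 0.0294 against 0.0294 at 5). Adding own baseline × time brought it to 0.0216 and 0.0222; the constrained model gave 0.0211 and 0.0200.

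**The case against.** The strongest reply is that the plan already contains the remedy. Its adjusted analysis includes interactions of the Table 7 covariates with time, and Table 7 lists the Aim 2 measures at baseline. Read literally, own baseline × time could be in the model. In 1,500 simulated trials with that term, the variance fell by a factor of 1.36 (constrained model 1.41) for 3 visits and 1.27 (1.34) for 5 visits under equal correlation, and by 1.60 (1.62) and 1.76 (1.96) under AR(1). So it would be wrong to infer that Table 7 cannot help. But the plan does not say that each outcome's own baseline is meant or that the adjusted analysis is primary. The unadjusted analysis recovers nothing, and most functional secondary outcomes are absent from Table 7.

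Other objections also narrow the point:

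- **Size.** A reader might take a quarter to a half as a fixed loss. It depends on a correlation of 0.5 and a structure the plan does not name. The 52% needs AR(1) with 0.5 per six months, a baseline-to-month-24 correlation of only 0.5⁴ = 0.06. With 0.5 per twelve months the 5-visit factor is 1.63.
- **Secondary outcomes.** The 0.5 is stated for TNFα and fasting glucose only. Stable measures such as body composition could lose far less, and DEXA is scheduled three times, not at every frailty visit.
- **Power.** A reader might infer that a test with 80% power would rise to 90% or more. No interaction test in the plan has a stated 80% power, and the glucose calculation gives no SD.
- **Bias.** Nothing here shows a biased estimate with complete data or an incorrect stated figure.
- **Linear slopes.** If a true difference of 1.0 appears early and stays flat, the slope scaled to 24 months reads 0.80–1.00 in the planned model and 1.00–1.19 in the constrained one. The constraint is not wholly without consequence if time stays linear.

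**Conclusion.** The point holds as one of efficiency. The Aim 2 first-step models, and the continuous secondary models that follow the same form, estimate a baseline arm difference that the design makes zero in expectation, and they read the effect from treatment × time alone. At correlation 0.5 the loss is 25–27% under equal correlation and 38–52% under AR(1), for 3 to 5 visits with complete data and linear time. It falls to 4–17% at correlation 0.9 and to 15–22% with the random slopes assumed above. For gait speed, 6-minute walk, SPPB, the frailty index and body composition these figures only illustrate the mechanism.

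The point does not extend to the Aim 1 frailty model. Under the random walk used for the Aim 1 power simulation, dropping the baseline difference gained almost nothing (variance factor 1.00–1.02).

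**What to change.** - **Main analysis.** For the Aim 2 first-step models and the continuous secondary outcomes, specify a constrained longitudinal model: time counted from baseline, a common baseline mean in both arms, no treatment main effect, treatment × time kept. Categorical visits are preferable, so that a non-linear effect does not distort a slope; name the contrast to be tested, for example the arm difference at month 24.
- **Covariance and schedule.** Name the covariance structure, and reconcile the three-visit and six-monthly schedules for plasma markers so that the modelled visits are fixed.
- **Covariates.** Say whether the unadjusted or adjusted analysis is primary, and whether own baseline × time is included in the adjusted one.
- **If post-baseline values are modelled instead,** with own baseline and baseline × visit as covariates, the tested quantity must become the adjusted arm difference at month 24 or averaged over visits. It must not remain the treatment × time slope: without the baseline visit, that slope has a variance 4.0 (equal correlation) or 2.5 (AR(1)) times the planned one at 3 visits, and 2.0 or 1.5 times at 5 visits.

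The cost is SAP rewording and, if linear time is kept, a slope that weights visits differently from the planned one under a non-linear effect. No new data, visits or participants are needed.
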